Research Aims to be studied in this protocol:

Aim 2) Compare uptake of genetic testing for patient-directed standard of care vs. enhanced standard of care genetic services delivery models for 1,920 unaffected primary care patients. We will utilize a randomized trial design with clinic-level randomization to compare two standard of care models: a *patient-directed standard of care* model and an *enhanced* model. In the *patient-directed* model those identified by the clinical decision support (CDS) infrastructure as meeting testing criteria will be informed of their cancer risks, provided with educational resources, and offered the option to select genetic testing through a patient portal. This online portal will be overseen by HCI genetic counselors. The *enhanced standard of care* model in which primary care providers and patients are notified through CDS when criteria are met (the *enhancement* of standard of care) and of the availability of standard of care genetic services. We will compare uptake of genetic testing by model and by race/ethnicity and rurality.

Aim 3) Compare adherence to recommendations and other patient responses for the genetic services delivery models. We will compare the effects of the genetic services delivery models on adherence to management recommendations at 12 months after return of results, or last genetic services contact. We will assess cognitive (i.e., recall, comprehension, uncertainty, risk perceptions) and affective (i.e., test-related distress, positive reactions, decision regret) responses at 4 weeks, and communication (i.e., family, provider) interactions at 4 weeks and 12 months after last genetic services contact. We will also examine differences in effects by race/ethnicity and rurality.

7. Is this a multi-site study, where more than one site needs IRB approval?

Yes No

8. Background and Introduction:

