Sample size for Aim 2 was calculated using PASS 15 based on an equivalence test for the difference of two proportions in a cluster-randomized design. Sample sizes of 480 in the patient-directed arm and 480 in enhanced standard of care arm, which were obtained by sampling 32 clusters (clinics) with 15 participants each and 16 clusters (clinics) with 30 participants each, respectively, achieve 80% power to detect equivalence. The margin of equivalence, given in terms of the difference between proportions, extends from -0.10 to 0.10. The calculations assume Likelihood Score Tests (Farrington & Manning) were used with an ICC of 0.05, and a significance level of 0.05. We believe that this is likely an overestimate of ICC based on our prior work. This sample size is sufficient for a multilevel multivariable regression analysis and achieves >95% power to detect a small effect size (0.02) attributable to 1 independent variable using an F-Test with an alpha of 0.05, adjusted for an additional 20 independent variables. To examine effect modification, sample size is calculated based on logistic regression of a binary response variable (Y) on a binary independent variable (X) and a binary confounder variable (Z). A sample size of 1,710 observations achieves 80% power at a 0.05 significance level to detect the X-Z interaction odds ratio of 1.5, using a two-sided Wald test. We will therefore enroll 1,920 patients in the Aim 2 trial to allow for about 10% attrition.

Aim 3 Analysis

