Aim 3 analysis will follow analytic procedures to address the dimension of Effectiveness from our conceptual framework. For comprehension, concordance between patient responses and information from genetic counselors' notes will be scored. We will test bivariate relationships between the outcome variables and study arm using Student's t-test or the nonparametric Wilcoxon rank-sum test between continuous variables, and chi-square test (or Fisher's exact test if small cell counts) for categorical data. We will examine distributions for continuous outcomes and transform the data if skewed. Procedures for building multilevel multivariable linear (continuous outcomes) or logistic (binary outcomes) regression models are described above. Regression models extended to include random effects for clinic or provider will be fit using software for linear mixed models for continuous outcomes and generalized linear mixed models for categorical outcomes. As with Aim 2, we will examine effect modification by testing for significant interactions between variables in regression models.

Aim 3 Sample Size

We estimate a sample size of 1,100 for a multilevel multivariable regression analysis with >90% power to detect a small effect size (0.02) attributable to 2 independent variables using an F-Test with an alpha of 0.05 using PASS 15 Software. The variables tested are adjusted for an additional 20 independent variables. To examine effect modification sample size is calculated based on logistic regression of a binary response variable (Y) on a binary independent variable (X) and a binary confounder variable (Z) with a sample size of 1,710 observations achieves 80% power at a 0.05 significance level to detect the X-Z interaction odds ratio of 1.5. Calculations assume that a two-sided Wald test is used.

IRB_00123563

Created: 6/5/2019 3:01
PM

IRB_00123563

- Request for Waiver of Consent

PI: [name]

Submitted: 3/5/2019

Title: Broadening the Reach, Impact, and
Delivery of Genetic Services**Request for Waiver or Alteration of Consent***** Requested Waivers**

Date Created	Type of Request	Purpose of Waiver Request
View 3/18/2019	Waiver of Informed Consent	Waiver of consent for chart review without patient contact

IRB_00123563

Created: 6/5/2019 3:01 PM

PI: [name]

Submitted: 3/5/2019

IRB_00123563

IRB Smart Form

Title: Broadening the Reach, Impact, and Delivery of Genetic Services

Request for Waiver or Alteration of Consent

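### Aim 3 plans its regressions at 1,100 patients but quotes interaction power only at Aim 2's 1,710, without showing how Aim 3 would reach that number

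*Combined protocol and SAP*

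**What the plan says.** All sample-size text is in section 4, Study Information, item 9.

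- **Aim 3 Sample Size, main regression.** "We estimate a sample size of 1,100 for a multilevel multivariable regression analysis with >90% power to detect a small effect size (0.02"; that effect is "attributable to 2 independent variables using an F-Test with an alpha of 0.05 using PASS 15 Software". The next sentence adds: "The variables tested are adjusted for an additional 20 independent variables".
- **Aim 3 Sample Size, effect modification.** The model is "logistic regression of a binary response variable (Y) on a binary independent variable (X) and a binary confounder variable (Z"; the calculation "with a sample size of 1,710 observations achieves 80% power at a 0.05 significance level to detect the X-Z interaction odds ratio of 1.5". The paragraph ends: "Calculations assume that a two-sided Wald test is used". It gives no outcome rate, no prevalence for X or Z, no clustering allowance, and no enrolment or attrition figure.
- **Aim 2 Sample Size.** The same 1,710, 80% and odds ratio of 1.5 appear here, followed by: "We will therefore enroll 1,920 patients in the Aim 2 trial to allow for about 10% attrition".
- **Aim 3 Analysis.** Effect modification is to be examined by testing interactions in regression models, linear for continuous outcomes and logistic for binary ones.
- **Section 1, item 6, Aim 3.** "We will also examine differences in effects by race/ethnicity and rurality".
- **Section 3, Participants, item 4.** The 1,920 is a count of consent cover letters sent.
- **Section 4, item 6, Research Procedures.** Several Questionnaire #1 outcomes, among them recall, comprehension and test-related distress, are collected only from patients who decide to test. Adherence also draws on health-record data, and up to 20,000 records may be tracked.

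**The concern.** A single paragraph uses two sample sizes for what appear to be the same models. The regressions are estimated at 1,100, the interactions are terms in regression models, and yet interaction power is given only at 1,710. That number is traceable to Aim 2, where it leads to the enrolment of 1,920. In Aim 3 it has no stated source.

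Differences by race/ethnicity and rurality are a stated part of Aim 3, and the Background gives disparities in access as a main rationale. A reader of the paragraph could take a non-significant Aim 3 interaction to come from a test with 80% power for an odds ratio of 1.5. If the analysis has 1,100 patients or fewer, that confidence is not earned, and an absence of evidence of modification is easily over-read.

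**Working it through.** **Inputs from the plan.** N = 1,100 and N = 1,710; interaction odds ratio 1.5, so ln 1.5 = 0.4055; two-sided alpha 0.05 (z = 1.960); 80% power (z = 0.842; sum 2.802); F-test effect size 0.02 with 2 tested and 20 adjusting variables; 1,920 letters; about 10% attrition, stated for Aim 2.

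**1. The main-regression figure.** Noncentral F with 2 and N − 23 degrees of freedom and noncentrality 0.02 × N. At N = 1,100 the noncentrality is 22 and power is 99.1%, so a claim of more than 90% is true for independent patients; 90% needs about 636.

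**2. The interaction figure at 1,710.** For a ratio of odds ratios, the variance of the log interaction is the sum over the four X–Z cells of 1/(N·w·p(1 − p)), where w is the cell share and p the outcome rate. Its minimum is 64/N, with equal cells and p = 0.5, so it bounds every choice of the unstated inputs.

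- SE at 1,710 = sqrt(64/1,710) = 0.1935; 0.4055/0.1935 = 2.096; power = Φ(2.096 − 1.960) = 55.4%.
- Smallest N for 80% = 64 × 2.802²/0.4055² ≈ 3,055.
- A grid search over prevalences, intercept and main effects found nothing below 3,072. A one-sided test gives at most 67.4% at 1,710.

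The stated 80% at 1,710 is therefore not reproduced.

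**3. Power at 1,100, accepting the plan's 80% at 1,710.** The noncentrality scales with the square root of N.

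- 2.802 × sqrt(1,100/1,710) = 2.247; power = Φ(2.247 − 1.960) = 61.3%, 19 points below 80%.
- Odds ratio detectable with 80% power = exp(0.4055 × sqrt(1,710/1,100)) = 1.66.

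**4. Power at 1,100, calculated directly.**

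- SE = sqrt(64/1,100) = 0.2412; 0.4055/0.2412 = 1.681; power = Φ(1.681 − 1.960) = 39.0% at most.
- Detectable odds ratio = exp(2.802 × 0.2412) = 1.97 at best.
- Illustrations with balanced arms and a common 30% outcome rate (assumptions): a 30% subgroup gives 29% power and a detectable odds ratio of 2.24; a 20% subgroup gives 23% and 2.51.

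Steps 3 and 4 rest on different premises, so their figures should not be combined.

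**5. How many replies each number needs.** 1,710/1,920 = 89%; 1,100/1,920 = 57%. The Aim 2 allowance gives 1,920 × 0.9 = 1,728, just above 1,710.

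**6. Clustering.** Steps 1 to 4 treat patients as independent. As an illustration, assume the 48 clinics of the Aim 2 calculation (32 + 16) and 1,100/48 ≈ 23 patients per clinic. With the Aim 2 ICC of 0.05, the design effect is 1 + (22.9 − 1) × 0.05 ≈ 2.1, the effective N about 525, and F-test power about 83%. ICCs of 0.01 to 0.03 give 97% to 91%.

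**The case against.** The strongest reply is that the paragraph attaches 80% to 1,710 and never claims it for 1,100. Aim 2 has the same layout: one N for the main comparison, a larger one for interactions, and enrolment set to cover the larger. Aim 3 could be read likewise, with 1,100 for main effects and 1,710 for interactions, both within 1,920. Adherence can draw on health-record data and so need not be limited by questionnaire return.

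Much of this stands. Three stronger inferences are tempting, and the documents do not support them:

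- *That every Aim 3 interaction test has 1,100 patients, so all of Aim 3 falls short by the same amount.* No section says so, and health-record adherence may be analysed in more.
- *That 1,100 must be the expected number because 636 suffices for the F-test.* With clustering, 1,100 could be a minimum: at an ICC of 0.03 it gives about 91%. No ICC is stated for Aim 3, so neither reading is established.
- *That the claim of more than 90% for the main regression is wrong.* It holds for independent patients.

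It is also fair that an interaction odds ratio describes only the binary outcomes, and that no section says a non-significant interaction will be read as no modification.

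The benign reading does not rescue the questionnaire outcomes. The 1,920 counts letters sent, so 1,710 would need about 89% to respond; the 10% allowance is stated for Aim 2 only; and outcomes asked only of tested patients have a smaller base still. Nor does granting 1,710 restore the figure, because the direct bound there is 55%.

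**Conclusion.** The point holds as a gap in the Aim 3 power statement: interaction power is quoted at an N that the paragraph neither plans for nor explains. Conditional on 1,100 patients in the interaction tests, power for an odds ratio of 1.5 is about 61% on the plan's own terms and at most 39% by direct calculation. If Aim 3 did have 1,710, the direct figure is at most 55%, so 80% is not delivered on either reading of N.

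The 61% assumes only that the plan's 80% at 1,710 is right. The 39% and 55% assume a two-sided Wald test, independent patients and an interaction defined as a ratio of odds ratios; they are upper bounds over the unstated outcome rate and prevalences, and unmodelled clustering would lower them. The gap is clearest for questionnaire outcomes. For health-record adherence the analysis N is simply not stated. This should be corrected, but it does not undermine the main Aim 3 comparisons.

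**What to change.** In the Aim 3 Sample Size text, replace the 1,710 statement with the interaction power, or the interaction detectable with 80% power, at the N expected for each outcome source:

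- questionnaire outcomes in all respondents;
- questionnaire outcomes collected only from tested patients;
- adherence from the health record.

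For each, give the assumed outcome rate and subgroup share. Use an interaction odds ratio for binary outcomes and a difference between subgroups in the arm mean difference for continuous ones. Use one consistent premise: either document the inputs behind 80% at 1,710 and scale from there, or recalculate directly. Say whether clustering is allowed for and, if not, that it lowers the figures.

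Report Aim 3 subgroup effects as arm differences with confidence intervals within each group, and state that a non-significant interaction is not evidence of no modification.

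The cost is rewriting and a short recalculation, with no extra patients or data. The downside is a less favourable stated power for Aim 3 effect modification.

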Multicenter Study:

Yes

Coordinating Center or Organization:

Huntsman Cancer Institute

Project Funding:

Sponsor	Sponsor Type	Sponsor Contact Information	Prime Sponsor	Prime Sponsor Type	OrgID
View NIH NATIONAL CANCER INSTITUTE	Federal Government	NCI Grants Management Specialist: [name] Email: [contact] [contact]			11259

Has the Funding Source granted approval to conduct this study:

Approved

1. Clinical Research Category (Select One):

Observational (OBS)

2. Primary Purpose of the Research (Select One):

Health Services Research (HSR)

3. Study Source (Select One):

Externally Peer-Reviewed: R01s, SPORES, U01s, U10s, P01s, CTEP, or any other clinical research study mechanism supported by the NIH or affiliate organizations (click HELP button for a full list)

4. Study Model Code (Select One):**5. Time Perspective Code (Select One):****6. Have project statistics been reviewed by a statistician:****7. How will accrual and demographic information be tracked:**

REDCap

8. Does this study target a Rare Disease (meaning it targets a cancer with an incident rate of = < 3 per 100,000 per year): Yes No**9. Number of subjects to be enrolled at the University of Utah in year 1:**

380

10. Estimated number of potentially eligible subjects seen at the University in the past year:

500

11. Source of data (e.g. CTRG estimate, cancer registry, clinic stats, TriNetX etc.):

FCAC clinic stats

12. Estimated time (in months) for full accrual at the University of Utah:

2.5 years

13. Is this study run through the HCI Clinical Trials Office:

No

14. Department overseeing this research:

Comments:

IRB_00123563

Created: 6/5/2019 3:01
PM

IRB_00123563

IRB Smart Form - Read Only

PI: [name]

Submitted: 3/5/2019

Title: Broadening the Reach, Impact, and Delivery
of Genetic Services

Sponsor Information

a. Sponsor:

NIH NATIONAL CANCER INSTITUTE

b. Sponsor Contact Information:*Address, phone number, fax number used for event reporting and study correspondence.*

NCI Grants Management Specialist: [name]
Email: [contact]
[contact]

c. If the funding type is "Federal Agency, or federal flow through", provide the following information:**Grant Number:**

1U01CA232826

Grant Awardee (Institution and Investigator):

University of Utah (lead) and NYU

Principal Investigators: [name] and [name] (Utah);
[name] (NYU)

Effective Start Date: 9/1/2018**Effective End Date:** 8/31/2023*If the grant has been awarded to the University of Utah, please attach a copy of the grant application to the Documents and Attachments page.***d. Are you working on this study with the University of Utah Office of Sponsored Projects to obtain this funding?**

Yes

If no, please explain:

A contract with the Office of Sponsored Projects may be required even if you are not receiving direct funds. Any relationship with an outside entity should be discussed with OSP:

Main Campus OSP: **[contact]**
UUHSC OSP: **[contact]**
VAMC OSP: **[contact] [name]**

IRB_00123563**Created:** 6/5/2019 3:01 PM**IRB_00123563** Finish

PI: [name]

Submitted: 3/5/2019**Title:** Broadening the Reach, Impact, and Delivery of Genetic Services

Finish Instructions

Finish Instructions

1. To view errors, select the "Validate" option at the top-left of the page. If you have errors on your application, you won't be able to submit it to the IRB.
2. Selecting the Finish button will NOT submit the application to the IRB. You MUST select the "Submit" option on the workspace once you've selected the "Finish" button.
3. If your study has a faculty sponsor: Once the PI submits the application, it will be sent to the faculty sponsor for final approval. The IRB cannot review the study until the faculty sponsor submits the application to the IRB.

Date: Monday, May 4, 2020 9:30:11 PM

[Print](#) [Close](#)**IRB_00115509 - CR_3/9/2020 2:18 PM****Created:** 3/9/2020 2:18 PM**PI:** [name]**Submitted:** 3/23/2020**Title:** Broadening the Reach, Impact, and Delivery of Genetic Services[HELP?](#)

1. Status

Overall, what is the enrollment status for this study?

Open to enrollment of new participants

•

IRB_00115509 - CR_3/9/2020 2:18 PM**Created:** 3/9/2020 2:18 PM**PI:** [name]**Submitted:** 3/23/2020**Title:** Broadening the Reach, Impact, and Delivery of Genetic Services[HELP?](#)

2. Progress of Study and Enrollment Information

Overall Study Enrollment Progress

Number of currently approved enrollments for this study as a whole: 1,920 consent cover letters sent; up to 20,000 EHR records

Number enrolled across all sites as of today's date: 0

- Describe the progress of the study, observations of the participants studied, and reason(s) for continuing the study:**

Progress for this study remains ongoing although delayed by the technical implementation timeline. Enrollment at the Utah site is expected to commence in April with NYU enrollment projected to begin in June.

The study team has completed building questionnaires in RedCap and is prepared to begin enrollment once patients have completed the necessary clinical procedures.

- What results (preliminary or final) have been obtained from the study? If the study is part of a multi-center trial, this should be stated and any available results provided. If there are no results that are appropriate to report to the IRB at this time, this should be stated and explained:**

Because this study has not enrolled any participants, there are no results to disclose at this point.

Please attach any abstracts or publications:

Name Version Date Created Date Modified Date Approved

There are no items to display

- Describe participant enrollment and its effect on the study design and scientific merit. If under-accrued, describe any plans for increasing enrollment during the next approval period. If a multicenter trial, also discuss enrollment at other sites.**

This study has no participants enrolled. Enrollment is expected to begin at Utah in April and at NYU in June.

IRB_00115509 - CR_3/9/2020 2:18 PM**Created: 3/9/2020 2:18 PM****PI:** [name]**Submitted: 3/23/2020****Title:** Broadening the Reach, Impact, and Delivery of Genetic Services**HELP?**

— Progress of Sites and Enrollment —

Select each site to update the enrollment information.**List of Study Controlled Locations**

	Site Name	Investigator's Name	Enrollments since Last CR	Enrollments as of Today	Non English Speakers	Withdrawn
View	NYU School of Medicine	[name]		0	0	0
View	University of Utah	[name]		0	0	0

IRB_00115509 - CR_3/9/2020 2:18 PM**Created: 3/9/2020 2:18 PM****PI:** [name]**Submitted: 3/23/2020****Title:** Broadening the Reach, Impact, and Delivery of Genetic Services**HELP?**

— 3. Problems & Events —

Provide narrative summary of any available information regarding adverse events which

- 1. have occurred since the last IRB review.**

- There have been no adverse events.

Have any additional risks to participation in this study been identified (from any site or**other relevant source) since last approval? If reports or amendments identifying additional**

- 2. risks have been submitted since last approval, please mark ◊yes◊.**

- Yes No

IRB_00115509 - CR_3/9/2020 2:18 PM**Created: 3/9/2020 2:18 PM****PI: [name]****Submitted: 3/23/2020****Title: Broadening the Reach, Impact, and Delivery of Genetic Services****HELP?****5. Amendments****A list of amendments associated with this study since the last approval date.**

Name Date Submitted IRB #

AM_Questionnaires and Pilot 10/7/2019 [AM_00035690](#)AM_Option to email participants and correct questionnaire typo 1/22/2020 [AM_00036697](#)**1. Are there any changes to be made now? (Including scientific design, procedures, participant population, or any minor changes.)** Yes No**IRB_00115509 - CR_3/9/2020 2:18 PM****Created: 3/9/2020 2:18 PM****PI: [name]****Submitted: 3/23/2020****Title: Broadening the Reach, Impact, and Delivery of Genetic Services****HELP?****6. Report Forms**

Name Date Submitted IRB #

IRB_00115509 - CR_3/9/2020 2:18 PM**Created: 3/9/2020 2:18 PM****PI: [name]****Submitted: 3/23/2020****Title: Broadening the Reach, Impact, and Delivery of Genetic Services****HELP?****7. Documents and Attachments****Approved eProtocol Summary:**

Name	Version	Date Created	Date Modified	Date Approved
ID00000007(0.01)	0.01	5/4/2020 11:28 AM	5/4/2020 11:28 AM	ID00000007

[Print View: IRB Draft Protocol Summary](#)

Updated eProtocol Summary:

Name	Version	Date Created
There are no items to display		

Date Modified

Date Approved

Approved Consent Forms:

Name	Version	Date Created	Date Modified	Date Approved
03_2020 BRIDGE consent cover letter V1.2(0.01)	0.01	3/12/2020 3:24 PM	3/12/2020 3:24 PM	5/4/2020 11:28 AM

Updated Consent Forms:

Name	Version	Date Created
There are no items to display		

Date Modified

Date Approved

Approved Parental Permission Forms:

Name	Version	Date Created
There are no items to display		

Date Modified

Date Approved

Updated Parental Permission Forms:

Name	Version	Date Created
There are no items to display		

Date Modified

Date Approved

Approved Assent Forms:

Name	Version	Date Created
There are no items to display		

Date Modified

Date Approved

Updated Assent Forms:

Name	Version	Date Created
There are no items to display		

Date Modified

Date Approved

Approved VA Consent Forms:

Name	Version	Date Created
There are no items to display		

Date Modified

Date Approved

Updated VA Consent Forms:

Name	Version	Date Created
There are no items to display		

Date Modified

Date Approved

Approved Surveys, etc.:

Name	Version	Date Created	Date Modified	Date Approved
Questionnaire #1 - Genetic Testing 10042019 Clean.docx(0.01)	0.01	10/4/2019 3:36 PM	10/4/2019 3:36 PM	11/4/2019 4:30 PM
Questionnaire #1 - No Genetic Testing 100319.docx(0.01)	0.01	10/4/2019 3:36 PM	10/4/2019 3:36 PM	11/4/2019 4:30 PM

Name

[Questionnaire #2 - No Genetic Testing 10042019 Clean.docx\(0.01\)](#)
[Questionnaire #2 - Genetic Testing Clean 011320\(0.01\)](#)

Name	Version	Date Created	Date Modified	Date Approved
	0.01	10/4/2019 3:37 PM	10/4/2019 3:37 PM	11/4/2019 4:30 PM
	0.01	1/13/2020 10:47 AM	1/13/2020 10:47 AM	1/22/2020 9:28 AM

Updated Surveys, etc.:

Name Version Date Created
 There are no items to display

Date Modified Date Approved

Approved Company Protocol:

Name Version Date Created
 There are no items to display

Date Modified Date Approved

Updated Company Protocol:

Name Version Date Created
 There are no items to display

Date Modified Date Approved

Approved Investigational Brochure:

Name Version Date Created
 There are no items to display

Date Modified Date Approved

Updated Investigational Brochure:

Name Version Date Created
 There are no items to display

Date Modified Date Approved

Approved Grant Application:

Name Version Date Created Date Modified Date Approved
[Grant application\(0.01\)](#) 0.01 1/20/2019 3:03 PM 1/20/2019 3:03 PM 6/5/2019 2:56 PM

Updated Grant Application:

Name Version Date Created
 There are no items to display

Date Modified Date Approved

Approved Literature/Cited References:

Name Version Date Created Date Modified Date Approved
[Background and Introduction References\(0.01\)](#) 0.01 2/22/2019 8:32 AM 2/22/2019 8:32 AM 6/5/2019 2:56 PM

Updated Literature/Cited References:

Name Version Date Created Date Modified Date Approved
 There are no items to display

Current PI Scholarly Record (CV/Resume):

Name	Version	Date Created	Date Modified	Date Approved
[name] CV(0.04)	0.04	4/2/2015 12:18 PM	8/27/2018 3:25 PM	

Updated PI Scholarly Record (CV/Resume):

Name	Version	Date Created	Date Modified	Date Approved
[name] CV(0.04)	0.04	4/2/2015 12:18 PM	8/27/2018 3:25 PM	

Current Faculty Sponsor Scholarly Record (CV/Resume):

Name	Version	Date Created	Date Modified	Date Approved
There are no items to display				

Updated Faculty Sponsor Scholarly Record (CV/Resume):

Name	Version	Date Created	Date Modified	Date Approved
There are no items to display				

Approved Other Stamped Documents:

Name	Version	Date Created	Date Modified	Date Approved
There are no items to display				

Updated Other Stamped Documents:

Name	Version	Date Created	Date Modified	Date Approved
There are no items to display				

Approved Recruitment Materials, Advertisements, etc.:

Name	Version	Date Created	Date Modified	Date Approved
Q1 invitation message.docx(0.01)	0.01	10/21/2019 12:20 PM	10/21/2019 12:20 PM	11/4/2019 4:30 PM
Q2 reminder message.docx(0.01)	0.01	10/21/2019 12:20 PM	10/21/2019 12:20 PM	11/4/2019 4:30 PM

Updated Recruitment Materials, Advertisements, etc.:

Name	Version	Date Created	Date Modified	Date Approved
There are no items to display				

Approved Other Documents:

Name	Version	Date Created	Date Modified	Date Approved
There are no items to display				

Updated Other Documents:

Name	Version	Date Created	Date Modified	Date Approved
There are no items to display				

PI: [name]**Submitted:** 3/23/2020**Title:** Broadening the Reach, Impact, and Delivery of Genetic Services**HELP?****8. Instructions and Finish**

1. To view errors in this application, select the "Hide/Show Errors" option at the top or bottom of the page. If you have errors on your application, you won't be able to submit it to the IRB.

Changes to the Update Study Application

2. Be sure to make all proposed changes to the Update Study portion of the application by selecting the "Update Study" button located on the left side of the amendment or continuing review workspace, which will be available once you select the "Finish" button at the top or bottom of this page.
3. To attach updated or new documents with this application, you may access the Documents and Attachments page in the Update Study application.
4. If you are proposing changes to any ancillary applications (i.e. RDRC-HUS or RGE), you must access these applications through the Update Study application on the Ancillary Applications page. All changes to ancillary applications must be approved by the corresponding committee prior to IRB approval of the amendment.

Submitting the Completed Continuing Review Application

5. Selecting the  button alone will NOT submit the application to the IRB. You MUST also select the "Submit" option on the workspace after you've selected the "Finish" button. Only the PI can submit the application to the IRB.
6. If your study has a faculty sponsor: Once the PI submits the application, it will be sent to the faculty sponsor for final approval. The IRB cannot review the study until the faculty sponsor submits the application to the IRB.

IRB_00115509 - CR_3/9/2020 2:18 PM**Created:** 3/9/2020 2:18 PM**PI:** [name]**Submitted:** 3/23/2020**Title:** Broadening the Reach, Impact, and Delivery of Genetic Services**Study Location Questions****NYU School of Medicine****Site Status****What is the enrollment status for this site?**

Open to enrollment of new participants

1,920 consent cover letters sent; up to 20,000 **Number of currently approved enrollments for this EHR records** **study as a whole**

Enrollment since the beginning of the study at this site:

0 Total number enrolled as of today's date at this site

Enrollment since the initial approval at this site:

How many non-English speakers have been enrolled?

0

How many participants signed consent forms but did not end up participating in the study?

0

Problems and Events

Have any unanticipated problems or adverse events involving risks to participants occurred since the last IRB approval?

Yes No

Have there been any complaints about the research since the last IRB review?

Yes No

Local HRPP Reporting

Have any significant financial conflicts of interest for study personnel been identified since the last approval that have not been reported to the IRB?

Yes No

Have there been any changes to human research protection reviews or approvals from your institution since last approval that have not been reported to the IRB?

Yes No

IRB_00115509 - CR_3/9/2020 2:18 PM

Created: 3/9/2020 2:18 PM

PI: [name]

Submitted: 3/23/2020

Title: Broadening the Reach, Impact, and Delivery of Genetic Services

Study Location Questions

University of Utah

Site Status

What is the enrollment status for this site?

Open to enrollment of new participants

1,920 consent cover letters sent; up to 20,000 **Number of currently approved enrollments for this EHR records** **study as a whole**

Enrollment since the beginning of the study at this site:

0 **Total number enrolled as of today♦s date at this site**

Enrollment since the initial approval at this site:

How many non-English speakers have been enrolled?

0

How many participants signed consent forms but did not end up participating in the study?

0

Problems and Events

Have any unanticipated problems or adverse events involving risks to participants occurred since the last IRB approval?

Yes No

Have there been any complaints about the research since the last IRB review?

Yes No

Date: Monday, March 29, 2021 9:31:05 PM

 IRB_00115509 - CR_2/22/2021 12:04 PM**Created:** 2/22/2021 12:04 PM**PI:** [name]**Submitted:** 3/16/2021**Title:** Broadening the Reach, Impact, and Delivery of Genetic Services**HELP?**

1. Status

Overall, what is the enrollment status for this study?

Open to enrollment of new participants

•

IRB_00115509 - CR_2/22/2021 12:04 PM**Created:** 2/22/2021 12:04 PM**PI:** [name]**Submitted:** 3/16/2021**Title:** Broadening the Reach, Impact, and Delivery of Genetic Services**HELP?**

2. Progress of Study and Enrollment Information

Overall Study Enrollment Progress

Number of currently approved enrollments for this study as a whole: 1,920 consent cover letters sent; up to 20,000 EHR records**Number enrolled across all sites at last Continuing Review:** 0**Number enrolled across all sites as of today's date:** 36**Number enrolled across all sites since last Continuing Review:** 36

- Describe the progress of the study, observations of the participants studied, and reason(s) for continuing the study:**

Utah began enrollment for their pilot study in April 2020 and enrollment for their full study in November 2020. To date, 81 participants have been invited to participate in Questionnaire #1 and 1 participant has been invited to participate in Questionnaire #2 at this site. Although delayed due to COVID-19, recruitment remains ongoing and enrollment is expected to pick up during 2021 now that the technical implementation has been completed.

NYU began enrollment for their pilot study in Dec 2020 and enrollment for the full study in February

2020. To date, 23 participants have been invited to participate in Questionnaire #1. The technical implementation was substantially delayed at this site was delayed due to COVID-19 but the study team is confident that they can still meet enrollment goals in the outlined timeframe.

- **What results (preliminary or final) have been obtained from the study? If the study is part of a multi-center trial, this should be stated and any available results provided. If there are no results that are appropriate to report to the IRB at this time, this should be stated and explained:**

There are no results to disclose at this point.

Please attach any abstracts or publications:

Name Version Date Created Date Modified Date Approved

There are no items to display

- **Describe participant enrollment and its effect on the study design and scientific merit. If under accrued, describe any plans for increasing enrollment during the next approval period. If a multicenter trial, also discuss enrollment at other sites.**

Although significantly delayed due to COVID-19 and technical implementation hurdles, enrollment at both sites has officially begun. Now that the technical infrastructure has been completed, tested, and implemented study teams at both sites anticipate the enrollment rate to increase substantially over the next approval period.

IRB_00115509 - CR_2/22/2021 12:04 PM

Created: 2/22/2021 12:04 PM

PI: [name]

Submitted: 3/16/2021

Title: Broadening the Reach, Impact, and Delivery of Genetic Services

HELP?

Progress of Sites and Enrollment

Select each site to update the enrollment information.

List of Study Controlled Locations

	Site Name	Investigator's Name	Enrollments since Last CR	Enrollments as of Today	Non English Speakers	Withdrawn
View	NYU School of Medicine	[name]	2	0	0	
View	University of Utah	[name]	34	34	0	0

IRB_00115509 - CR_2/22/2021 12:04 PM

Created: 2/22/2021 12:04 PM

PI: [name]

Submitted: 3/16/2021

Title: Broadening the Reach, Impact, and Delivery of Genetic Services

HELP?

3. Problems & Events

Provide narrative summary of any available information regarding adverse events which

1. have occurred since the last IRB review.

- There have been no adverse events.

Have any additional risks to participation in this study been identified (from any site or other relevant source) since last approval? If reports or amendments identifying additional

2. risks have been submitted since last approval, please mark yes no.

- Yes No

IRB_00115509 - CR_2/22/2021 12:04 PM

Created: 2/22/2021 12:04 PM

PI: [name]

Submitted: 3/16/2021

Title: Broadening the Reach, Impact, and Delivery of Genetic Services

HELP?

5. Amendments

A list of amendments associated with this study since the last approval date.

Name	Date Submitted	IRB #
------	----------------	-------

AM Adding COVID items to questionnaires	5/18/2020	AM_00038160
---	-----------	-----------------------------

AM Questionnaire outreach and study personnel changes	7/15/2020	AM_00038525
---	-----------	-----------------------------

AM Spanish Translations	9/2/2020	AM_00039151
-------------------------	----------	-----------------------------

AM Questionnaire outreach	10/19/2020	AM_00039559
---------------------------	------------	-----------------------------

1. Are there any changes to be made now? (Including scientific design, procedures, participant population, or any minor changes.)

- Yes No

IRB_00115509 - CR_2/22/2021 12:04 PM

Created: 2/22/2021 12:04 PM

PI: [name]

Submitted: 3/16/2021

Title: Broadening the Reach, Impact, and Delivery of Genetic Services

HELP?

Amendment Description

1. Type of Amendment (check all that apply):

Administrative changes, for example:

Changes to study procedures, for example:

Other changes

2. What changes are being made? List and number each change, grouping similar changes together.

1. Administrative Changes

1. Remove [name] and [name]

2. Move personnel from guest to study staff

1. [name]

2. [name]

3. [name]

4. [name]

3. Add [name] as study staff

2. Changes to study procedures

a. Study staff will track COVID-related appointments and diagnoses for patients who were identified by the algorithm.

3. Other changes

1. Update of study category in PRMC application.

3. Describe the reason for each of the changes described above. List and number the reasons according to the list above.

1. Administrative Changes

1. [name] is no longer at HCI

2. Guests have had an influence on study design and will be included as authors on publications moving forward

3. [name] should be added to be up to date with study staff

2. Changes to study procedures

a. COVID-related experiences may impact the way patients use and interact with the health system, including genetic services. We would like to report if patients' experience with COVID may have impacted their decision to receive counseling or testing.

3. Other changes

1. The study category in the PRMC application will be updated as requested by the CCSG/HCI internal reporting team. We have not made any changes to the study design.

4. How does each change described above effect participants? List and number the effects according to the list above.

1. Administrative changes will have no effect on participants

2. Changes to study procedures

a. Tracking COVID-related appointments and diagnoses would not directly affect participants.

3. Other changes

1. Changing study category will not affect participants.

5. Will the modification(s), in the opinion of the local PI, increase or decrease the risk to participants?

Neither

